## 7.7. Sample Size Analysis

Details concerning the Bayesian simulations for this study were previously reviewed (**Bayesian Simulations Memo, Version 4.1, May 5, 2015**).

### 7.7.1. Objective 1: 5-Year Superiority

These simulations were used to evaluate the power and type 1 error for determining superiority of coflex in conjunction with surgical decompression relative to surgical decompression alone at Month 60. For the purpose of these simulations it was assumed that the Month 60 success rate would be 0.57 for coflex®. The prior distribution derived in the Memo is beta(82.1,62.1) reflecting a 20% discount off of a total prior sample size of N=179. Power was found to be equal to 83% if the true superiority margin is 12.5%. If the true superiority margin is only 10%, then power to conclude superiority is reduced to 65%. Type 1 error was determined through simulation by assuming that the probabilities of Month 60 success were equal to 0.57 for both treatment groups. The estimated type 1 error rate is equal to 0.037(SD=0.0011) based on an average of 10 identical simulations with varying randomization seeds.

It may be now be noted that subsequent to the Bayesian design memo submission, the final results from the PMA study were submitted to FDA in the Final Report (P110008/R014). The Month 60 PAS CCS was achieved in 55.9% (104/186) patients which is very close to the projected success rate of 57%. The total sample size of 186 is slightly larger than the assumed 179 which implies a discount of the prior of 23% rather than 20%. Sensitivity analyses (see Table 4 from Bayesian Memo) were provided that demonstrate that type 1 error is 0.040, still below 0.05, if the true success rate is 56% rather than 57%.

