	
<math>CCS_{decomp}) > 0</math>. Superiority will be concluded if the posterior probability is at least equal to 0.95.
 
Objective 4: (real conditions of use): The following hypotheses will be tested in order to evaluate whether or not coflex® device performance is clinically inferior in the PAS population compared to the IDE population using a non-inferiority <math>\delta=-0.1175</math>. The following hypotheses will be tested.
 
Ho: <math>CCS_{PAS} \leq CCS_{IDE} - 0.1175</math>
 
Ha: <math>CCS_{PAS} > CCS_{IDE} - 0.1175</math>.
 
Non-inferiority of coflex performance in the PAS population will be concluded if the posterior probability that (<math>CCS_{PAS} > CCS_{IDE} - 0.1175</math>) is at least 0.95.
 
Sample Size Analysis Details concerning the Bayesian simulations for this study were previously reviewed and are included in Bayesian Simulations Memo, Version 4.1, May 5, 2015.
 
Objective 1: (5-year superiority) These Simulations were used to evaluate the power and type 1 error for determining superiority of coflex® in conjunction with surgical decompression relative to surgical decompression alone at Month 60. For the purpose of these simulations it was assumed that the Month 60 success rate would be 0.57 for coflex®. A posterior probability threshold of at least 0.95 was selected. Power was found to be equal to 83% if the true superiority margin is 12.5%. If the true superiority margin is only 10%, then power to conclude superiority is reduced to 65%. Type 1 error was determined through simulation by assuming that the probabilities of Month 60 success were equal to 0.57 for both device groups. The estimated type 1 error rate is equal to 0.037(SD=0.0011) based on an average of 10 identical simulations with varying randomization seeds.
 
Objective 2: (2-year non-inferiority) Bayesian simulations were performed to evaluate the operating characteristics for testing the Objective 1 hypothesis non-inferiority hypothesis. In the pivotal IDE study, 135 of 204 patients (66.2%) achieved Month 24 CCS. These results were used to define the prior distribution for coflex in conjunction with surgical decompression as beta (135.5, 69.5) since the distribution prior to the IDE trial was specified as beta (0.5, 0.5). This Jeffries non-informative prior was assumed for patients undergoing decompression alone. A non-inferiority margin of -0.10 is specified. Non-inferiority will be concluded if the Bayesian posterior probability that (<math>CCS_{coflex+decomp} - CCS_{decomp}) > -0.10</math> is at least equal to 0.95. When evaluating

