**Ho:  $CCS_{coflex+decomp.} - CCS_{decomp} \leq 0$  (not superior)**  
**Ha:  $CCS_{coflex+decomp.} - CCS_{decomp} > 0$  (superior)**

An informative prior based on final 5-year IDE study results for the coflex group will be used as described below. A non-informative prior will be used for the decompression alone group. The Bayesian posterior probability that  $(CCS_{coflex+decomp.} - CCS_{decomp.}) > 0$  will be determined.

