$F_{p,t,j,r}$  = Number of Month 60 failures for subjects in subclass p, in treatment group t, who were successes (r=1) or failures (r=0) at follow-up time j.

Note that these transition beta distributions assume non-informative prior distributions to allow only the observed data to impact on the multiple imputations (i.e., all a and b are set to 1). Subsequently, the informative prior on the study device group is applied to determine the posterior distribution of non-inferiority.

In order to implement the Bayesian Multiple Imputation algorithm, the following steps will be used.

1. For each patient that has not completed follow-up, a value  $\pi_i$  is randomly chosen from  $\Pi_{p,t,j,r} \sim \beta(1 + S_{p,t,j,r}, 1 + F_{p,t,j,r})$  corresponding to their PS subclass, treatment group, and success-failure status at their last known follow-up; this value represents the probability that the subject is a success at 60-months.
2. Using this randomly chosen  $\pi_i$ , the patient is then assigned a success (1) or failure (0) from a random draw of the binomial distribution  $Bin(n, p)$  with  $n = 1$  and  $p = \pi_i$ .
3. Steps 1-2 are repeated for all subjects with incomplete follow-up, separately for each treatment group and propensity score subclass.
4. Using the resulting completed datasets (containing both observed and imputed values at month 60), the PS-adjusted total number of successes ( $S_t$ ) and failures ( $F_t$ ) at month 60 are calculated for each treatment group using the average of PS subclasses as described above. The probability of success for each treatment is then chosen randomly from the resulting posterior beta distributions incorporating the informative prior in the study device group and the non-informative prior for controls. The distribution of the difference in success probabilities is therefore:

$$\pi_S - \pi_D \sim \beta(82.1 + S_t, 62.1 + F_t) - \beta(1 + S_D, 1 + F_D)$$

5. Step 4 is repeated ( $n = 10,000$  times), to obtain the posterior distribution of the differences in treatment success ( $\pi_S - \pi_D$ ), and the posterior probability of non-inferiority is calculated as the proportion of times that  $\pi_S - \pi_D \geq -\delta$ .
6. To complete the multiple imputation and obtain the final posterior non-inferiority probabilities, steps 1-5 are repeated 20 times and the final posterior probability is determined as the average of the 20 multiple imputations.

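### The Objective 1 coflex prior is said to rest on the final 5-year IDE results, but beta(82.1,62.1) comes from the earlier 57%-of-179 projection

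*Combined protocol and SAP*

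**What the plan says.** Section 7.3 (Objective 1) names the source of the prior but gives no numbers: "An informative prior based on final 5-year IDE study results for the coflex group will be used as described below".

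The only numerical Objective 1 prior that follows is in Section 7.7.1, taken from the Bayesian Simulations Memo: "beta(82.1,62.1) reflecting a 20% discount off of a total prior sample size of N=179". The planning rate is in the same paragraph: "it was assumed that the Month 60 success rate would be 0.57 for coflex". Step 4 of Section 7.11.1 puts those parameters into the primary analysis as "82.1 + S_t, 62.1 + F_t".

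The second paragraph of 7.7.1 was added after the memo. It reports the final Month 60 result as "55.9% (104/186) patients which is very close to the projected success rate of 57" percent. It then re-describes the prior's weight against 186 patients, "which implies a discount of the prior of 23% rather than 20" percent, and cites a memo table showing that "type 1 error is 0.040, still below 0.05, if the true success rate is 56% rather than 57" percent. It does not recompute the prior, and it does not say that the projected prior is kept on purpose.

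**The concern.** The prior in the primary decision rule does not match its stated source. The bridging remark in 7.7.1 makes it look as though the final data have been absorbed, but only the size of the prior was compared with the final data, not its success fraction.

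This is the Objective 1 test, and the prior carries almost as much weight as the 150 new coflex patients. An analyst who follows 7.3 literally would build a prior from 104/186; one who follows 7.11.1 would use 82.1 and 62.1. In a close result the two could reach opposite conclusions. If the choice were settled only after the outcomes were known, it would be open to challenge.

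**Working it through.** **Inputs.** From 7.7.1: projected rate 0.57, N = 179, 20% discount, final result 104/186. From the synopsis, sample size for Objective 1: "A posterior probability threshold of at least 0.95 was selected". From 4.2: 150 patients per group. Control prior: beta(1,1) as coded in 7.11.1, and also Jeffreys beta(0.5,0.5), the control prior named for Objective 2 in 7.7.2. I take 104/186 to be the final 5-year IDE result meant in 7.3.

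**1. Where the coded prior comes from.**
- Successes: 0.5 + 0.8 × 179 × 0.57 = 82.1
- Failures: 0.5 + 0.8 × 179 × 0.43 = 62.1

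Both parameters reproduce. The prior is the projection plus a Jeffreys start.

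**2. The 23% statement.** The weight is 0.8 × 179 = 143.2 patients, and 1 − 143.2/186 = 0.230. This also reproduces.

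**3. What that statement leaves out.**
- Successes retained: 81.6/104 = 78.5%
- Failures retained: 61.6/82 = 75.1%
- Prior mean: 82.1/144.2 = 0.569, against 104/186 = 0.559

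A uniform 23% discount would keep 77% of each.

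**4. Prior rebuilt from 104/186.**
- 23% discount: 143.2 × 104/186 + 0.5 = 80.6 and 143.2 × 82/186 + 0.5 = 63.6
- 20% discount: 0.8 × 186 = 148.8, so 148.8 × 104/186 + 0.5 = 83.7 and 148.8 × 82/186 + 0.5 = 66.1

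**5. Operating characteristics.** I enumerated all 151 × 151 outcomes and declared superiority when the posterior probability that the coflex rate exceeds the control rate was at least 0.95. Ranges cover the two control priors. Propensity-score adjustment and imputation were not modelled.

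| Quantity | Stated | beta(82.1,62.1) | beta(80.6,63.6) |
|---|---|---|---|
| Power, coflex 57%, 12.5% margin | 83% | 82% | 80% |
| Power, coflex 57%, 10% margin | 65% | 65% | 61% |
| Power, coflex 55.9%, 12.5% margin | – | 85% | 83% |
| Power, coflex 55.9%, 10% margin | – | 69% | 65–66% |
| Type 1 error, both 57% | 0.037 | 0.035–0.036 | 0.028 |
| Type 1 error, both 56% | 0.040 | 0.044–0.045 | 0.036 |
| Type 1 error, both 55.9% | – | 0.045–0.046 | 0.037 |
| Type 1 error, both 55% | – | 0.055–0.056 | 0.045–0.046 |

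The stated power and the type 1 error at 57% are reproduced to within about a point and about 0.002 respectively.

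**6. Decision boundary.** With 67/150 control successes, superiority needs 74 coflex successes under the coded prior, 75 under beta(83.7,66.1) and 76 under beta(80.6,63.6). Between 60 and 80 control successes, the gap between the coded prior and either rebuilt prior is one or two coflex successes. For given trial data, the coflex posterior mean differs by (82.1 − 80.6)/(144.2 + 150), about 0.5 percentage points.

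**The case against.** The best defence is that the plan is open about this and can be executed. Section 7.3 gives no numbers and points forward, and only one numerical prior follows, the same in 7.7.1 and 7.11.1. Section 7.7.1 reports the final result, calls it close to the projection, restates the weight and cites a sensitivity figure. A reader could take this as a decision to keep a prior that had already been reviewed. That stands in part: the plan does not contain two competing numerical priors, and no arithmetic in 7.7.1 is wrong. But the decision to keep the projected prior is nowhere stated, and 7.3 says otherwise.

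Three stronger readings are tempting, and the documents do not support them.

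- **The stated power is 3 to 4 points too high.** The figures of 80% and 61% pair a prior centred on 55.9% with a true coflex rate of 57%. The design sets prior mean and assumed rate together. Moving both to 55.9% gives about 83% and 65–66%, which is what the plan states.
- **The type 1 error of 0.040 at 56% is wrong.** It comes from a table in the memo, which is not among the documents. Holding the prior fixed gives 0.044–0.045 and re-centring it gives 0.036. The stated value lies between them, and how it was obtained cannot be determined.
- **Only beta(80.6,63.6) is correct.** The 23% describes what follows from leaving the prior unchanged. The discount chosen at design was 20%, which gives about beta(83.7,66.1).

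**Conclusion.** The point holds as a mismatch between the stated source of the Objective 1 prior and the prior actually coded. The coded prior mean is 0.569 where the final data give 0.559, and the difference favours coflex. The effect is small: one or two coflex successes in 150 at the boundary, about half a point in the posterior mean, and just under 0.01 in type 1 error at a common rate of 56%.

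A reader might infer that the decision rule is materially too lenient. The figures do not show that: with the coded prior, type 1 error is below 0.05 at the projected 57% and at the observed 55.9%. The margin is thin, though. At a common rate of 55%, under one point below the IDE result, it is 0.055–0.056, against 0.045–0.046 with the rebuilt prior at 23%.

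These figures assume 150 evaluable patients per arm and no propensity-score adjustment or imputation.

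**What to change.** Before Month 60 outcomes are unblinded, choose one of two routes and make 7.3, 7.7.1 and step 4 of 7.11.1 agree.

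- **Re-derive.** Replace beta(82.1,62.1) in 7.7.1 and 7.11.1 by the prior computed from 104/186, and state the discount: 23% gives beta(80.6,63.6), 20% gives about beta(83.7,66.1). For the 23% version, report power of about 83% and 65–66% and type 1 error of about 0.037 at a true coflex rate of 55.9%, with about 80% and 61% power at 57%.
- **Retain.** Correct 7.3 to say that the projected memo prior is deliberately kept, and say in 7.7.1 that the 23% refers to weight only. Report type 1 error of about 0.045 at 56% and 0.055–0.056 at 55%, and check the stated 0.040 against the memo, saying whether that table held the prior fixed.

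The cost is wording plus a rerun of the existing simulation for the chosen prior. Sample size and data collection do not change.

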### 4.2. Number of Subjects

The numbers of patients to be enrolled is 150 patients per group (300 total). This total will be increased by 15% to account for loss-to-follow-up. The sample sizes were increased by an additional 20% in control group and 5% in the study device group to account for trimming of control patients and possible trimming of study device patients during the propensity score design. Therefore, the total enrolled will be 186 coflex patients and 220 decompression control patients for a total enrollment of 406.

Patients will be enrolled into one of the treatment groups (Group A, without additional implant, Group B, with coflex® Interlaminar Technology).

Recruitment of about 5 patients per month is expected. Each site will be required to enroll at least 5 patients.

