### 7.7.2. Objective 2: 2-Year Non-Inferiority

Bayesian simulations were performed to evaluate the operating characteristics for testing the Objective 2 non-inferiority hypothesis. In the pivotal IDE study, 135 of 204 patients (66.2%) achieved Month 24 CCS. These results were used to define the prior distribution for coflex® in conjunction with surgical decompression as beta (135.5, 69.5) since the distribution prior to the IDE trial was specified as beta (0.5, 0.5). This Jeffries non-informative prior was assumed for patients undergoing decompression alone. A non-inferiority margin of -0.10 is specified. Non-inferiority will be concluded if the Bayesian posterior probability that ( $CCS_{coflex+decomp.} - CCS_{decomp.} > -0.10$ ) is at least equal to 0.95. When evaluating statistical power, it was assumed that the true success rate 0.662 for patients treated with coflex®. However, preliminary results from the German decompression study suggest some an advantage of coflex® over decompression alone. Therefore, when evaluating power, Month 24 CCS for decompression alone was assumed to be at least 2% lower, or 0.642. In contrast, Type 1 error was evaluated by assuming that the coflex® success rate 0.662 but that the success rate for decompression was 0.10 larger. With N=150 patients per group, power was shown to be 89%; and type 1 error was shown to be 0.042 and 0.052 'prior to the prior' and with the prior engaged, respectively.

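### Objective 1 type 1 error at a true rate of 56% is stated as 0.040; the design in the plan gives about 0.044 to 0.045, and the error reaches 0.05 at a common rate of about 55.5%

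*Combined protocol and SAP*

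**What the plan says.** Objective 1 tests Month 60 superiority of coflex plus decompression over decompression alone. In the Synopsis (Sample Size Analysis, Objective 1): "A posterior probability threshold of at least 0.95 was selected". Section 7.7.1 gives the coflex prior: "The prior distribution derived in the Memo is beta(82.1,62.1) reflecting a 20% discount off of a total prior sample size of N=179". For the controls, section 7.3 says: "A non-informative prior will be used for the decompression alone group". Section 4.2 sets the size: "The numbers of patients to be enrolled is 150 patients per group (300 total").

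Section 7.7.1 then reports power of 83% for a true margin of 12.5 points and 65% for 10 points, with coflex at 57%. With both groups at 57%, "The estimated type 1 error rate is equal to 0.037(SD=0.0011) based on an average of 10 identical simulations" run with different seeds.

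The same section adds that the final IDE result was 104/186 (55.9%). It does not move the prior to that result. It re-reads the discount, "which implies a discount of the prior of 23% rather than 20" per cent, and the analysis formula in section 7.11.1 still uses 82.1 and 62.1. It then cites Table 4 of the Bayesian Memo for sensitivity analyses that "demonstrate that type 1 error is 0.040, still below 0.05, if the true success rate is 56% rather than 57" per cent. The documents give no Objective 1 type 1 error for any true rate below 56%.

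**The concern.** With an informative prior on one arm only, the false-positive rate rises as the true common rate falls below the prior mean, here 82.1/144.2 = 56.9%. The plan's own figures imply a rise of only 0.003 for the first point of shortfall (0.037 at 57%, 0.040 at 56%). The stated design implies about 0.009.

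The figure matters because it is the only one in the documents that shows how the Objective 1 false-positive rate behaves once the IDE rate fell below projection. Coflex doing somewhat worse in this study than in the IDE study is a possibility the plan itself sets out to examine under Objective 4. A reader who extrapolates from 0.037 and 0.040 would think that several points of shortfall could be absorbed before 0.05 is reached.

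**Working it through.** **Inputs**

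- Coflex prior beta(82.1, 62.1) (section 7.7.1). It equals 0.5 + 0.8 × 102 and 0.5 + 0.8 × 77, that is, 102 successes and 77 failures out of 179 at 80% weight. The re-read discount agrees: (144.2 − 1)/186 = 0.77, or 23% off.
- Control prior beta(a, a). Section 7.3 gives no parameters. Section 7.7.2 specifies Jeffreys for Objective 2 ("This Jeffries non-informative prior was assumed for patients undergoing decompression alone"), so a = 0.5. The Month 60 formula in section 7.11.1 uses a = 1. Both were run.
- 150 per group; threshold 0.95.

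**Formula**

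For s coflex and d control successes, superiority is concluded when

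P(π_S > π_D) ≥ 0.95, with π_S ~ beta(82.1 + s, 62.1 + 150 − s) and π_D ~ beta(a + d, a + 150 − d).

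The probability of concluding superiority is the sum of Bin(s; 150, p_S) × Bin(d; 150, p_D) over all of the 151 × 151 outcomes that meet this rule. Type 1 error sets p_S = p_D.

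**Step 1: the plan's base case**

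| Quantity | Plan | a = 0.5 | a = 1 |
|---|---|---|---|
| Power, 57% v 44.5% | 83% | 82.2% | 82.3% |
| Power, 57% v 47% | 65% | 64.6% | 64.7% |
| Type 1 error, both 57% | 0.037 | 0.0352 | 0.0360 |

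If the posterior probability is itself estimated from 1,000 draws, the error at 57% is 0.0366 to 0.0370. The model therefore matches the stated design closely.

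**Step 2: the same model at lower common rates**

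| True common rate | Plan | a = 0.5 | a = 1 |
|---|---|---|---|
| 56% | 0.040 | 0.0441 | 0.0450 |
| 55.9% | not given | 0.0451 | 0.0460 |
| 55.5% | not given | 0.0492 | 0.0502 |
| 55% | not given | 0.0549 | 0.0558 |

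The rise from 57% to 56% is 0.0441 − 0.0352 = 0.0089 (a = 0.5) or 0.0450 − 0.0360 = 0.0090 (a = 1). A value of 0.040 belongs to a true rate of about 56.4% to 56.5%. A simulation of 400,000 trials with a = 0.5 agrees: 0.0437 at 56% and 0.0550 at 55%.

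**Step 3: where the error reaches 0.05**

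The crossing is at 55.43% (a = 0.5) or 55.52% (a = 1). The final IDE rate is 104/186 = 55.91%, so the distance is 55.91 − 55.43 = 0.48 or 55.91 − 55.52 = 0.39 points. With a simulated posterior (1,000 to 10,000 draws) the crossing is slightly higher, at 55.55% to 55.67%.

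**Step 4: could another setting give 0.040 at 56%?**

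- Group sizes from 100 to 220 per arm: never below 0.0433.
- Weight on the IDE data from 0 to 100%: never below 0.0434.
- Simulated posterior: 0.045 to 0.047, which is further from 0.040.
- Prior re-centred on 104/186: about 0.036, which misses on the other side and is not what the plan does.

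**The case against.** The strongest objection is that the plan does not derive 0.040; it reports it from Table 4 of a memo that is not part of the documents. The inputs of that table are unknown, and a nearby prior does give the figure. With 101 rather than 102 successes out of 179 at the same discount, the prior is beta(81.3, 62.9) and the error at 56% is 0.0400 to 0.0408. That is not the stated prior, however. It also spoils the base case, giving about 0.032 at 57% and power of about 81% and 63%, against the stated 0.037, 83% and 65%. What stands is that the memo may describe another scenario, so a reader should not infer that Table 4 is itself wrong. The documents support only the statement that 0.040 does not follow from the design written in the plan.

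Second, simulation error. The SD of 0.0011 is given only for the 57% case, and the plan does not say whether it is the spread between runs or the SD of the average. On the first reading 0.040 lies (0.0441 − 0.040)/0.0011 = 3.7 SDs from the exact value. On the second, a single run has an SD of 0.0011 × √10 = 0.0035, and 0.040 lies about 1.2 SDs away. This remains open. It could explain how the figure arose, but it would not make 0.040 the error rate of the design.

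Third, the conclusion drawn in section 7.7.1 survives. A reader might infer from the corrected figure that type 1 error is not controlled at the observed IDE rate. It is: 0.044 to 0.045 at 56% and 0.045 to 0.046 at 55.9% are all below 0.05. Nor does the plan call the margin comfortable; it says only that the error is below 0.05.

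Finally, the position of the crossing relative to 55.5% depends on the control prior, so "about" is as precise as the documents allow. Error that rises below the prior mean is a general property of such designs, and section 7.7.2 openly reports 0.052 for Objective 2.

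**Conclusion.** The point holds as an error in a stated figure. For the design written in the plan, Objective 1 type 1 error at a true common rate of 56% is about 0.044 to 0.045, not 0.040, a difference of 0.004 to 0.005. The margin is thinner than the stated figure suggests: about 55.5% is the lowest true common rate at which the error stays below 0.05.

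This rests on 150 analysed patients per group, the prior beta(82.1, 62.1), a beta(0.5,0.5) or beta(1,1) control prior and a threshold of 0.95. Propensity-score averaging and multiple imputation are not modelled, although the plan's base case is closely matched without them. The 55.5% limit is therefore a property of the simulated design and has not been shown for the full primary analysis.

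**What to change.** In section 7.7.1, check 0.040 against Table 4 of the Bayesian Memo and state that table's inputs (prior, group sizes, control prior, number of simulated trials). If Table 4 describes another scenario, say so. For the design as stated, replace 0.040 with about 0.044 to 0.045.

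Add one sentence: error below 0.05 holds only for a true common Month 60 success rate of about 55.5% or more, calculated without propensity-score averaging or imputation. Name the control prior for Objective 1 so that the figure can be reproduced. A curve of the error rate from 50% to 60% would be useful but is optional.

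The cost is a text correction and a slightly less favourable figure. The prior, threshold and sample size need not change.
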